Phase	
Pivotal

Description of Sites/Facilities Enrolling Participants	
Subjects will be enrolled at up to approximately 10 study sites and surgeries will be performed in ambulatory surgery centers or hospitals. All study sites and surgery centers will be located in the United States. Each site will be encouraged to randomize a minimum of 20 subjects, and no site will randomize more than 25% of the total number of randomized subjects.

Description of Study Intervention	
The study intervention is an IOL to be implanted unilaterally via routine small incision cataract surgery. Subject eyes in the test arm will be implanted with an investigational Toric Monofocal IOL with toricity of 1.5 D (in the IOL plane), while the eyes in the control arm will be implanted with a commercially available monofocal non-toric IOL. IOLs are implantable medical devices intended for long term use over the lifetime of the subject.

Study Duration	
Study duration is estimated to be approximately 20 months based on an estimated enrollment period of 8 months, subject participation period of 9 months (calculated as the maximum difference between the time of the Preoperative Visit to completion of Form 4), and 3 months for study close-out, database-lock and Investigative report.

Participant Duration	It is estimated that the duration of each subject's participation in the study will be approximately 9 months (calculated as the difference between the time of the Preoperative Visit to completion of Form 4).

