#### 8.4 UNSCHEDULED VISITS

Unscheduled visits are those which are not required by the study protocol, but which occur due to an ocular intervention or a subject complaint.

If a subject visit occurs between any regularly scheduled visits, this visit is to be documented as an Unscheduled Visit. During all unscheduled visits, the Investigator should conduct assessments as appropriate given the subject's condition. Recommended assessments include:

- Concomitant medication
- Manifest refraction
- BCDVA at 4 m- Photopic, Monocular (ETDRS) for study eye
- UCDVA at 4 m- Photopic, Monocular (ETDRS) for study eye
- Keratometry
- Slit lamp exam
- IOL observations
- IOL tilt and decentration grading
- Intraocular pressure (IOP)
- IOL Axis Orientation (retro-illuminated slit lamp photo in a **dilated** eye, only for subjects implanted with PODEYE TORIC IOL)
- Dilated Fundus Exam
- Adverse events
- Device deficiencies

The Investigator may perform additional procedures for proper diagnosis and treatment of the subject according to SOA in Section 1.3. The Investigator must document this information in the subject's source documents and record it on the USV eCRF.

If, during an Unscheduled Visit, the subject is discontinuing from the study, the Investigator must complete the Exit CRF.

Visits intended to fulfill scheduled visit requirements that fall outside the designated scheduled visit window are not Unscheduled Visits. In these cases, the visit data will be collected and transcribed to the appropriate scheduled visit CRF, and a protocol deviation should be reported, if applicable.

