## 9.7 MISSING DATA AND IMPUTATION

Missing Form 4 effectiveness endpoint data will be imputed for All-implanted and ITT analyses.

For ITT, All-implanted, and PP analyses, per ANSI Z80.30-2018, eyes that have a secondary surgery that is targeted to correct for postoperative toric IOL rotation shall have their clinical results prior to that surgical intervention carried forward as the final results for analysis. Further, in cases where axis misalignment measured at follow up visits after an SSI is greater than the axis misalignment prior to SSI,

the greater misalignment error shall be considered as the final result for analysis. Repositioning of toric IOLs will result in imputation of worst observed value or assignment failure for the co-primary endpoints at Form 4 analysis, as appropriate. Imputation methods described below will retain these worst-value or failure assignments and will not overwrite them with imputed values.

The primary imputation method for all co-primary endpoints will be by multiple imputation where details of initial seed, predictors and methods will be fully described in the Statistical Analysis Plan. Co-primary endpoint 1, will use 50 imputed datasets for analysis; all other endpoints, being binary and tested by exact methods, are not amenable to combining multiple imputations, so only the first imputed dataset will be used.

In addition, for co-primary endpoint 1, where two arms are involved, a tipping point sensitivity analysis will involve initially setting all control-lens eyes with missing data to the best observed outcome (presumably, 0.0 residual cylinder) and setting all toric-lens eyes with missing data to the worst observed outcome. The best and worst values will be incremented/decremented by 0.125 D until control eyes have the worst and toric have the best value imputed. The point at which, if any, where the results of the hypothesis test changes its results regarding rejection of the null hypothesis will be reported.

For all other co-primary endpoints, the tipping-point sensitivity analysis will be performed in which missing data are initially assumed to be failures. Then, one of the imputed failures will be imputed as a success. Then, a second failure will be assigned to a success. This process will be repeated until all missing data are imputed as successes. The point at which, if any, where the results of the hypothesis test changes its results regarding rejection of the null hypothesis will be reported.

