7.2 VISIT WINDOW

The visit schedule and the visit window for each visit are outlined in **Table 1**. The visit schedule applies to all subjects in both test and control groups.

Table 1 VISIT SCHEDULE

Visit	Visit Window
Preoperative	1 to 90 days prior to surgery in the study eye
Form 0 (Operative)	Day 0
Form 1	1 to 2 days following surgery in the study eye
Form 2	7 to 14 days following surgery in the study eye
Form 3	30 to 60 days following surgery in the study eye
Form 4	120 to 180 days following surgery in the study eye

Unscheduled visits will occur as needed, due to an ocular intervention or a subject complaint regarding their eye. Recommended assessments at unscheduled visits are listed in Section 8.4 of the study protocol. In the event of missing data at a scheduled visit, unscheduled visit results within the visit window will be used as replacements for any uncollected data. If more than one unscheduled visit falls within the window, then the unscheduled visit closest to the target date will be used. If two visits are equidistant from the target, then the latter of the two will be selected.

A summary of all examinations required at each visit is provided in the schedule of activities in Appendix A.

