7.2.1 Missing Observations

If no scheduled or unscheduled visit data are available within a visit window, the visit will be considered to be missed. Imputation will be performed in the ITT and All-implanted analysis populations, as described in Section 7.4.3.

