8.4.3 Imputation Methods and Sensitivity Analyses for Co-Primary Effectiveness Endpoints

For ITT and All-implanted analyses, per ANSI Z80.30-2018, eyes that have a secondary surgery that is targeted to correct for postoperative toric IOL rotation shall have their clinical results prior to that surgical intervention carried forward as the final results for analysis. Further, in cases where axis misalignment measured at follow up visits after a secondary surgical intervention (SSI) is greater than the axis misalignment prior to SSI, the greater misalignment error shall be considered as the final result for analysis. Repositioning of test IOLs will result in imputation of worst observed value or assignment failure for the co-primary endpoints at Form 4 analysis, as appropriate. Imputation methods described below will retain these worst-value or failure assignments and will not overwrite them with imputed values.

For the ITT and All-implanted analysis populations missing co-primary endpoint data will be imputed where there are no available data at Form 4. The primary imputation method will be by

multiple imputation and be implemented using the MI and MI ANALYSE procedure in SAS® (Version 9.4 or later) or using the mice package (Version 3.16.0 or later) from R. A pre-specified seed of 20231026 (the date of version 1.0 of the protocol) will be used. Predictors will include attempted toric correction, age, and sex; 50 imputed datasets will be generated; the Markov Chain Monte Carlo (MCMC) method will be applied when using SAS. [REDACTED]

[REDACTED]

[REDACTED]

[REDACTED]

For all other co-primary endpoints, the [REDACTED] will be performed in which missing data are initially assumed to be failures. Then, one of the imputed failures will be imputed as a success. Then, a second failure will be assigned to a success. This process will be repeated until all missing data are imputed as successes. The point at which, if any, where the results of the hypothesis test changes its results regarding rejection of the null hypothesis will be reported.

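### The visible imputation model names no postoperative measurement and no treatment arm, and the SAP and protocol disagree on whether an out-of-window Form 4 value counts as observed

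*SAP*

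**What the plan says.** **Imputation model.** Protocol 9.7 makes multiple imputation the primary method and promises that "initial seed, predictors and methods will be fully described in the Statistical Analysis Plan". SAP 8.4.3 then states: "Predictors will include attempted toric correction, age, and sex", with 50 imputed datasets. Redacted blocks follow in the same section. Protocol 9.7 adds that the binary co-primary endpoints use only the first imputed dataset.

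**What counts as missing.** SAP 7.2 sets the Form 4 window at "120 to 180 days following surgery in the study eye". SAP 7.2.1 says: "If no scheduled or unscheduled visit data are available within a visit window, the visit will be considered to be missed". It then sends such visits to imputation in ITT and All-implanted (its cross-reference is to a Section 7.4.3; the imputation section is 8.4.3). Protocol 8.4 says a scheduled visit that falls outside its window is not an unscheduled visit, and that "the visit data will be collected and transcribed to the appropriate scheduled visit CRF". SAP 8.4.3 imputes only where Form 4 data are unavailable and does not mention the window.

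**Protected eyes.** Under SAP 8.4.3, eyes operated on for rotation keep their pre-surgery result, or the larger misalignment if it is worse afterwards. Repositioned eyes keep a worst-value or failure assignment, which imputation may not overwrite.

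**The concern.** Imputation recovers information only through its predictors. The test arm receives one toric power (1.5 D in the IOL plane, 1.03 D at the cornea), so attempted toric correction varies little within that arm. Age and sex are then the only other named predictors for the toric-only endpoints. An eye well off axis at Form 3 that drops out would be imputed at about the rate of the completers. Co-primary endpoint 4 is the change in orientation from Form 3 to Form 4, so one of its two components is not named as a predictor.

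The window rule adds a second route. A Form 4 measured a few days early or late sits on the Form 4 CRF, yet under SAP 7.2.1 it may be replaced by a draw from the model.

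Both routes feed the primary ITT analysis. For the binary endpoints the replacement is a single random draw.

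**Working it through.** **1. The plan's own figures.**
- Joint power: 0.94 × 0.99 × 0.99 × 0.99 = 0.912, which reproduces the stated 91%.
- Completers: 230 × 0.87 = 200.1, which reproduces the stated 200. Missing toric eyes: 115 × 0.13 = 14.95, about 15.
- Exact power with the upper-bound rule (one-sided 95%), at n = 100 and n = 115: above 0.999 at both for endpoint 3 (99% against 95%), and 0.989 and 0.991 for endpoint 4 (91.46% against 90%). Both agree with the stated 99%.
- The 94% for endpoint 1 cannot be recomputed because its inputs are redacted.

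**2. Collected against named.**

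| Variable | Collected (Schedule of Activities) | Named in SAP 8.4.3 |
|---|---|---|
| IOL axis orientation | Forms 0, 1, 2, 3 | no |
| Manifest refraction | Preop, Forms 2, 3 | no |
| Keratometry | Preop, Form 3 | no |
| Treatment arm | at randomization | no |
| Attempted toric correction, age, sex | Preop | yes |

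**3. A Form 4 measured outside Day 120-180.** SAP 7.2.1 makes it missed and imputed. Under Protocol 8.4 it is recorded as Form 4. Under the SAP 8.4.3 trigger it is arguably available, so not imputed. SAP Section 2 lets SAP methods supersede the protocol's statistical methods, so Protocol 8.4 does not settle the matter, and the SAP's own two sections do not agree.

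**4. Size, binary endpoints.** Inputs: 115 toric eyes, 100 observed, 15 missing, one-sided 95% Clopper-Pearson upper bound. All failure rates below are assumptions, except that 1% and 8.54% are the complements of the protocol's planned 99% and 91.46%.

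Allowed failures, c:
- 95% target: 105/115 has upper bound 0.952 (passes) and 104/115 has 0.945 (fails), so c = 10.
- 90% target: 98/115 has 0.904 (passes) and 97/115 has 0.896 (fails), so c = 17.

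Let X ~ Bin(100, f_c) be failures among completers and f_m the failure rate among missing eyes.
- True outcomes: P(X + Y ≤ c), with Y ~ Bin(15, f_m).
- Imputation blind to the eye's own data: Σ P(X = x) · P(Bin(15, x/100) ≤ c − x).

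| Target | f_c | f_m | Expected failures, true / imputed | Pass, true | Pass, imputed |
|---|---|---|---|---|---|
| 95% | 5% | 5% | 5.75 / 5.75 | 0.97 | 0.95 |
| 95% | 5% | 20% | 8.0 / 5.75 | 0.83 | 0.95 |
| 95% | 5% | 40% | 11.0 / 5.75 | 0.44 | 0.95 |
| 95% | 1% | 20% | 4.0 / 1.15 | 0.999 | 1.000 |
| 90% | 8.54% | 20% | 11.5 / 9.8 | 0.96 | 0.98 |
| 90% | 8.54% | 40% | 14.5 / 9.8 | 0.81 | 0.98 |

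Example, row 2: 100 × 0.05 + 15 × 0.20 = 8.0 true failures expected, against 115 × 0.05 = 5.75 after imputation. The true-outcome column is the most that better predictors could recover. Imputation from Form 1-3 data would fall between the two columns.

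**5. Size, endpoint 1.** A simulation assumed an SD of 0.4 D, a Form 3 to Form 4 correlation of 0.5 to 0.9, and dropout that rises with Form 3 cylinder. Ignoring Form 3 biased the toric mean low by 0.01 to 0.05 D. Regressing on Form 3 brought the bias to about zero. When dropout did not depend on Form 3 cylinder, there was no bias either way.

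**The case against.** The strongest reply is that the list is not shown to be complete. The SAP says predictors will include three variables, and redacted text follows at once. That stands: it cannot be said that only these three are used. But Protocol 9.7 promised a full description in the SAP, and the visible sentence names no earlier measurement.

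Second, a reader might infer that the arms are imputed from one distribution, shrinking a 0.40 D difference to 0.87 × 0.40 = 0.35 D. That needs attempted correction not to distinguish the arms, for example a preoperative calculator value carried for control eyes too. The control lens is non-toric, so its attempted correction is naturally zero, and the variable would then stand in for arm. The visible SAP text does not say which coding applies, so the figure is conditional. The shrinkage would also work against the sponsor.

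Third, a reader might say that known failures are turned into successes. Repositioned eyes and eyes operated on for rotation are protected, and a failing Form 3 reading is not a known Form 4 failure. What remains is the out-of-window Form 4 failure and the uncorrected eye whose last reading failed.

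Fourth, the tipping-point analysis for the binary endpoints starts with all missing values as failures, and the PP analysis does not impute. Both would expose reliance on imputed successes, but neither changes the primary result. Finally, no document suggests that missing eyes do worse. With equal 5% failure rates, the blind method passes slightly less often (0.95 against 0.97).

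**Conclusion.** The point holds as a low-cost improvement and a needed clarification. The visible imputation model leaves out the measurements most likely to predict Form 4, and the texts conflict on whether a measured out-of-window Form 4 is observed.

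The effect on the conclusion is conditional. It inflates the chance of success only if missing eyes do worse than completers: at the 95% target, 0.83 becomes 0.95 with failure rates of 5% and 20%, and 0.44 becomes 0.95 with 5% and 40%. With completers at the planned 99% success rate and missing eyes failing 20%, almost nothing changes. These results rest on 15 missing toric eyes, a one-sided 95% bound and assumed failure rates. Out-of-window visits would add to the 15 only under the literal reading of SAP 7.2.1.

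A reader might also conclude that toric eyes never implanted, or explanted for reasons other than rotation, must be counted as failures. The documents do not support that. It is an estimand choice, and the endpoint definitions and hypotheses are redacted.

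**What to change.** 1. **SAP 8.4.3.** Impute the continuous quantities: residual cylinder in dioptres, and axis misalignment and orientation in degrees. Do this by arm or with arm in the model. Add the same eye's available Form 1-3 axis values, Form 2-3 manifest cylinder and preoperative keratometric cylinder to the named predictors. Then dichotomise. Keep the existing protection for repositioned and rotation-surgery eyes. State how attempted toric correction is coded for control eyes. If the redacted text already covers any of this, confirm it.
2. **SAP 7.2.1.** State that a measured out-of-window Form 4 counts as observed in ITT and All-implanted, in line with Protocol 8.4 and the 8.4.3 trigger. Add an in-window-only analysis as supportive, and correct the cross-reference to 8.4.3.

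The cost is SAP wording and some programming, settled before unmasking. The variables are already collected. The downside is less uniform timing of Form 4 in the primary analysis, which the in-window analysis would show.

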## 9.8 STATISTICAL TESTING OF EFFECTIVENESS ENDPOINTS

For co-primary endpoint 1, the test of superiority of the toric lens over the control lens to result in less residual cylinder, a Wilcoxon rank-sum test will be performed, given that the distribution of residual cylinder will be discrete and likely skewed, the t-test is used only as a preliminary estimate of the needed sample size. Given the loss of power due to the use of a non-parametric test, an assumed loss of power of 5% has been made to accommodate lower power of the Wilcoxon test. The point estimate of the difference and a 95% confidence interval of the treatment effect will be provided based on the mean difference and its standard error.

For co-primary endpoints, where axis stability is examined, the upper 95% boundary of a Clopper-Pearson confidence interval will be used to test if the null hypothesis can be rejected. Number and percentage of eyes achieving various levels of stability will be summarized.

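### SAP 8.4.3 names a multivariate-normal imputation model (SAS MCMC) that does not suit the co-primary endpoints, and leaves open whether SAS or R mice is primary; the effect on the verdict at the planned rates is small

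*SAP*

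**What the plan says.** **Method and software.** SAP 8.4.3 applies multiple imputation in the ITT and All-implanted populations: "missing co-primary endpoint data will be imputed where there are no available data at Form 4". The software is SAS PROC MI "or using the mice package (Version 3.16.0 or later) from R". The only method named in readable text is for SAS: "the Markov Chain Monte Carlo (MCMC) method will be applied when using SAS". No mice method is readable. Redacted blocks follow that sentence directly.

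**Settings.** One fixed seed, 20231026, is given for either package. On the content of the model the SAP states: "Predictors will include attempted toric correction, age, and sex; 50 imputed datasets will be generated".

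**Which package is primary.** SAP 8.4.3 does not say. SAP 9 lists SAS first and adds that other software, including R, may be used.

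**Nature of the endpoints.** Protocol 9.7 describes co-primaries 2 to 4 as "all other endpoints, being binary and tested by exact methods" and analyses them from the first imputed dataset only. Protocol 9.8 chooses the Wilcoxon test for co-primary 1 "given that the distribution of residual cylinder will be discrete and likely skewed". Protocol 9.7 also leaves the details of the imputation methods to the SAP.

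**Role.** ITT with imputation is the primary effectiveness analysis (SAP 7.1). SAP 6.2 plans 115 eyes per arm and expects 13% not to complete.

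**The concern.** The named method and the described endpoints do not match. A normal draw for a pass/fail outcome is a number such as 0.87 or 1.06, which an exact binomial test cannot count. A normal draw for a non-negative cylinder can fall below zero, and would then rank ahead of a perfect 0.00 D in the Wilcoxon test.

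The choice of package is a second gap. SAS MCMC and chained equations in mice are different algorithms, and one seed does not give the same random draws in both. For the binary endpoints a single dataset is used, so nothing averages out the luck of the draw. Two analysts could both follow the plan and report different primary counts. At stake are the reproducibility of the primary result and a model that can be defended for about 15 missing toric eyes.

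**Working it through.** **Inputs.** Assumed success is 99.0% against a 95% target (co-primary 3) and 91.46% against 90% (co-primary 4). The pass rule is that the upper Clopper-Pearson bound reaches the target (Protocol 9.5). Toric arm 115 eyes, 13% missing (SAP 6.2): 115 × 0.13 = 14.95, so 100 observed and 15 imputed. The mean and SD of cylinder are not readable and are assumed below.

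**1. The plan's own figures.** 0.94 × 0.99³ = 0.912, matching 91%. With two-sided 95% (or one-sided 95%) bounds and n = 115, co-primary 3 passes at 104 (105) eyes, power 1.000. Co-primary 4 passes at 97 (98) eyes, power 0.996 (0.991). These agree with the stated 99% to within about 1 point.

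**2. Normal draws for a 0/1 outcome, unrounded.** Simulated with three predictors unrelated to outcome, every imputed value was neither 0 nor 1. The share above 1 was 39% at a true rate of 91.46% and 46% at 99%.

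**3. If such draws were rounded at 0.5.** The imputed failure share is Φ((0.5 − p)/√(p(1 − p))).
- p = 0.9146: Φ(−0.4146/0.2795) = Φ(−1.483) = 6.9%, against 8.5%. Difference 1.64 points; 15 × 0.0164 = 0.25 eye; 0.25/115 = 0.21 points.
- p = 0.99: Φ(−0.49/0.0995) = Φ(−4.925), about 4 per 10 million, against 1%. 15 × 0.01 = 0.15 eye; 0.15/115 = 0.13 points.
- The direction is not constant. At p = 0.86, Φ(−0.36/0.347) = Φ(−1.038) = 15.0%, against 14%, so failures are then slightly over-imputed.

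**4. Set against the pass mark.** Co-primary 4 passes at 97/115 = 84.3% or 98/115 = 85.2%, which is 7.1 or 6.2 points below 91.46%. The shift uses 0.21/7.1 = 3.0% to 0.21/6.2 = 3.4% of that margin.

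**5. Negative cylinder.** Values were simulated as gamma, rounded to 0.25 D, then imputed by a normal model without bounds:

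| Assumed mean / SD (D) | Negative share | Of 15 eyes |
|---|---|---|
| 0.3 / 0.3 | 18% | 2.8 |
| 0.4 / 0.3 | 11% | 1.6 |
| 0.5 / 0.35 | 9% | 1.4 |
| 0.8 / 0.45 | 5% | 0.7 |
| 0.9 / 0.4 | 2% | 0.3 |

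**6. Count and verdict.** Rounded-normal imputation was compared with Bernoulli-type imputation (a stand-in for a logistic model or predictive mean matching), one dataset each.
- The success count differed in about 20% of trials at 99% and 69% at 91.46%.
- The pass/fail verdict differed in 0.0% (co-primary 3) and 1.2% (co-primary 4) at the planned rates, 2% to 3% when the true rate equals the target, and 13% to 15% when it is 4 to 6 points below.
- Pass rates under the two models differed by at most 2.2 points (66.9% against 64.7%, true rate 91%, target 95%).

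**7. How much of step 6 is the model.** Two independent draws from one binomial model differ with probability 1 − Σ P(k)², k = 0 to 15, P from Binomial(15, p). This gives 24% at p = 0.99 and 73% at p = 0.9146, about as often as in step 6. Repeating the verdict comparison with two Bernoulli-type draws (40,000 trials) gave disagreement of 0.0% and 1.2% at the planned rates and 13% to 15% at 4 to 6 points below target. Nearly all the disagreement therefore comes from resting on one draw, which a change of package alters just as a change of seed would.

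**The case against.** **Redaction.** The text after the MCMC sentence is blacked out and may specify rounding, bounds, a transformation, an R method or imputation in degrees. A reader might infer that the plan certainly produces fractional successes and negative cylinder. The documents do not support that: both arise only if pass/fail and raw cylinder are imputed directly without repair. This part of the objection stands. Such repairs would not make the normal model a good fit, however. Rounding has the bias in step 3, and a plain log transform fails if 0.00 D occurs, which Protocol 9.7 expects.

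**Which variable is imputed.** No readable text says that 0/1 outcomes are imputed, so a general shift of the axis endpoints towards success is not shown. The definition of co-primary 2 is redacted, so it cannot be called an axis endpoint. Both points stand.

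**Size.** A reader might set 0.21 points against the 1.46-point gap between 91.46% and 90% and call it 15% of the margin. Under the plan's pass rule the margin is 6 to 7 points, so the share is about 3%.

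**Rank test.** In a separate simulation (gamma shape 1.6, 100 observed and 15 imputed per arm), leaving negative values or clipping them at zero changed the Wilcoxon verdict in 0% of runs at arm means near 0.4 and 0.75 to 0.775 D, and in at most 0.9% for smaller differences. No material harm is shown.

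**Software.** A reader might infer that the primary result depends on the package. Different counts are possible; a different verdict is rare at the planned rates.

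**Tipping-point analyses.** These step missing outcomes from worst to best case, so they would expose a fragile result. They do not say which primary result to report.

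**Conclusion.** The point holds as a mismatch between stated method and stated endpoints, together with an open choice of package. Readable text names a multivariate-normal model for outcomes that the protocol itself describes as binary or as discrete and skewed, and permits a second package with no rule of precedence.

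The numerical consequence is small. If 0/1 outcomes are imputed and rounded, the bias at the assumed rates is about 0.15 to 0.25 eye of 115. The verdict on co-primaries 3 and 4 changes in about 0% to 1% of simulated trials at the planned rates. It reaches 13% to 15% only when the true rate is several points below target, and that comes mainly from using a single imputed dataset.

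These figures assume 15 missing toric eyes, data missing at random, predictors unrelated to outcome, and no covariates in the verdict simulation. The range for negative cylinder rests on assumed means and SDs. For co-primary 1, the planned effect and SD are not readable, so its verdict could be examined only under assumed values. The unredacted SAP may already meet part of the point.

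**What to change.** In SAP 8.4.3:

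1. Name one package for the primary analysis and tie the seed to it.
2. Replace MCMC with chained equations, using predictive mean matching for residual cylinder, so that every imputed value is one that was observed.
3. For co-primaries 3 and 4, impute the axis values in degrees by predictive mean matching and derive pass/fail from them. Keep the failure and worst-value assignments already planned for repositioned lenses.
4. For co-primary 2, impute its underlying measurement in the same way, or use a logistic model if only pass/fail exists.
5. Check these changes against the unredacted text and finalise them before unmasking.

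The cost is SAP wording and a changed procedure call. No new data are needed, and sample size and power do not change. Success rates may come out marginally less favourable.
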